8.1 Statistical and Analytical Plans (SAP)

Statistical analysis of the data will be formed at the conclusion of the study. Study examiners will be blinded until the results have been completed.

8.2 Statistical Hypotheses

Our hypothesis is that the sensitivity and specificity of the RRT in detecting posterior ocular abnormalities in children will be poor in lighted or dim room lighting conditions or following pharmacologic dilation.

The null hypothesis is that the sensitivity and specificity of the RRT for detecting posterior ocular abnormalities in children will improve significantly under dim room lighting conditions and/or following pharmacologic dilation.

8.3 Analysis Datasets

The baseline demographic data will be presented descriptively. Continuous data will be summarized as mean with standard deviation or median with interquartile range depending on the distribution of the data. Categorical data will be summarized using frequencies with percentage. Summary demographic statistics between patients with and without eye abnormalities will be compared using unpaired t-test (normal) and/or Mann-Whitney U test (skewed) for continuous data, and Chi-square test and/or Fisher's exact test (if any of the expected cell frequencies are <5) for categorical data. Normality assumption will be checked by using statistical test (e.g., Shapiro Wilk test) as well as graphical methods (e.g., histogram, q-q plot).

8.4 Description of Statistical Methods

To assess our primary and secondary hypothesis, sensitivity and specificity of the red reflex test (RRT) will be determined along with their 95% confidence interval using contingency tables for both anterior and posterior segment pathology. Positive predictive value (PPV), negative predictive value (NPV), and area under ROC curve (AUC) will also be determined. We will also compare sensitivity and specificity of RRT for both anterior and posterior pathology between with and without pharmacologic dilation using two-sided McNemar's test for correlated proportions.

All statistical tests will be two-sided and will be performed at the 5% level of significance unless otherwise stated. Stata 15.1 software will be used for all statistical analyses.

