2.1 Background Information and Relevant Literature

The early detection of ophthalmic pathology is critical for the prevention of vision loss and systemic morbidity in rare cases. The American Academy of Pediatrics (AAP), the American Association for Pediatric Ophthalmology and Strabismus (AAPOS), the American Academy of Ophthalmology (AAO), and the American Association of Certified Orthoptists (AACO) continue to advocate for inclusion of the red reflex test (RRT) as part of the ophthalmologic screening exam in the general pediatrics clinic. However, studies to date have demonstrated that there are potential limitations to the RRT, especially in its ability to accurately and reliably detect posterior segment pathology.

Standard procedure for the RRT currently involves viewing both eyes at arms length in lighted room followed by a darkened room to assess for symmetry of the reflection in terms of brightness and color. If an abnormality is suspected, then the operator may move closer for further inspection. With its current application, the RRT introduces subjectivity in interpretation and likely variation in pupillary reflection based on factors such as, the specific lighting condition, degree of physiologic dilation, and patient movement. Differences in operator experience with the RRT may further compound the shortcomings of this exam technique. These factors unfortunately reduce the accuracy and reliability of the RRT as a screening measure.

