2.2 Scientific Rationale

Question: Is the RRT a sensitive or specific screening tool for detecting anterior or posterior segment pathology under physiologic conditions or following pupillary dilation in the pediatric population?

Hypothesis: The RRT is not a sensitive or specific screening tool for detecting anterior or posterior segment pathology in the pediatric population even following pharmacologic pupillary dilation.

Visual acuity and disease are difficult to assess in the pediatric population and especially younger children due to normal developmental changes as well as

challenges in patient cooperation or symptom reporting. However, assessing visual and anatomic abnormalities in this age group remains of paramount importance to avoid visual morbidity, and rarely systemic complications, from undetected ophthalmic pathology. The RRT is currently recommended by the Joint Committee as an initial screening test for anterior and posterior segment ocular abnormalities in the pediatric population. The recommendations suggest that dim room lighting aids in the accuracy of the RRT. However, limited available evidence to date has demonstrated that the RRT is not a sensitive or specific test for detecting posterior segment pathology. Furthermore, there are no studies to date specifically examining the effect of dim lighting conditions or pupillary dilation on the sensitivity and specificity of the RRT.

This study aims to evaluate the sensitivity and specificity of the RRT for detecting anterior or posterior segment pathology in both ambient and dark lighting conditions, before and after pharmacologic dilation.

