5.1 Study Population, Recruitment and Retention

Pediatric patients will be recruited through clinical practice at the designated study sites. Participants with known anterior segment or posterior segment pathology will be eligible for inclusion. Patients who have a history of disease, treatments and/or surgical procedures affecting the ability for normal pupillary reaction are excluded. An equal number of age matched participants with a normal anterior and posterior segment exam will be recruited from routine outpatient clinic visits. Informed consent will be obtained and will include an option to be considered for medical photography. Participants may opt out of photography and still be included in the study. For Spanish speaking participants, a telephone interpreter will be used for study recruitment and informed consent. A Spanish informed consent (developed by a Spanish medical translator from our English written consent) will be provided. Current estimated number of subjects required for the study is 200 total including 100 controls. Patient charts will be accessed from date of birth to patient's current age using either Cerner or Epic depending on the study site location. Examiners will include ophthalmology residents with one completed year of ophthalmology training. They will be blinded to participants' ophthalmologic history.

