5.2 Inclusion Criteria

There is no difference in criteria for screening and enrollment. Patients with general eyelid pathology, ptosis, corneal pathology, astigmatism, cataract, vitreous pathology, vitreous detachment, vitreous hemorrhage, retinal pathology, retinopathy of prematurity, retinal detachment, retinal tear, retinal hemorrhage, retinoblastoma, other intraocular tumors overlying or outside of the central visual axis, retinal pigmented epithelial cell pathology, choroidal pathology, optic nerve pathology, retinal artery or vein pathology may be included.

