5.3 Exclusion Criteria

Patients who have a history of disease, treatments and/or surgical procedures affecting the ability for normal pupillary reaction are excluded.

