5.5 Recruitment

Subjects will be recruited through clinical practice at Children's National Health System and its Fairfax outpatient site. Subjects will be identified by the PI, [name], Vice-Chair, Department of Ophthalmology, in a review of medical records after a HIPAA authorization waiver for recruitment is granted. Subjects will be approached at a clinical care visit or an IRB approved study information letter will be sent to the participant's legally authorized representative (LAR). If the LAR expresses interest in the study, a copy of the IRB approved consent will be provided to the LAR. The informed consent will be signed by the LAR and assent will be obtained from the patient at an in-person visit before any research procedures or interventions are done.

The privacy of patients received for screening will be protected by password file encryption on Children's National Health System computers/hardware and will be viewable only to the PI, treating physicians and study staff. All study data that have been de-identified and requiring transport will be done in an encrypted flash memory drive.

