6.4 Description of Study Procedures/Evaluations

- *Medical history—ocular history from prenatal care and on will be obtained through the medical record or in person.*
- *Medication history—Current medications taken required.*
- *Physical examinations—Subject's red reflex and pupillary size will be examined using a direct ophthalmoscope in bright and dim room lighting conditions as well as before and after pharmacologic dilation. Automated vision screening using the Spot photoscreener will be performed before and after dilation.*
- *The results of the red reflex exam will be discussed with the patient during the clinic visit.*
- *Photographs of the subject's red reflex may be taken and edited to ensure anonymity. These photographs will allow for digital analysis of the patients red reflex. These photographs will be kept on password*

protected computers at Children's National Health System and on password protected encrypted flash drives. These photographs may be used for dissemination of study results such as in conference abstracts and medical journals. Once the study is complete, original photographs may be destroyed.

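### Sensitivity is estimated over all known cases with no record of how each was first detected, so eyes that reached the clinic through an abnormal red reflex can raise it relative to a screening population

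*Combined protocol and SAP*

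**What the plan says.** Section 2.2 poses a screening question: "Is the RRT a sensitive or specific screening tool for detecting anterior or posterior segment pathology". Section 2.1 notes that the professional bodies "continue to advocate for inclusion of the red reflex test (RRT) as part of the ophthalmologic screening exam in the general pediatrics clinic", and 2.2 adds that the test is the recommended initial screen.

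Under 5.1, "Participants with known anterior segment or posterior segment pathology will be eligible for inclusion". Section 5.5 adds that "Subjects will be recruited through clinical practice at Children's National Health System and its Fairfax outpatient site", with subjects identified by review of medical records. Section 5.2 is a list of diagnoses, and 5.3 gives the only exclusion: "Patients who have a history of disease, treatments and/or surgical procedures affecting the ability for normal pupillary reaction are excluded". None of these sections refers to how the pathology was first found.

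Section 8.4 gives the estimator: "sensitivity and specificity of the red reflex test (RRT) will be determined along with their 95% confidence interval using contingency tables", by segment, with McNemar's test comparing the RRT with and without dilation. Section 8.6, on minimizing bias, deals only with examiner blinding. Section 6.4 provides that "ocular history from prenatal care and on will be obtained through the medical record or in person", but no route-of-detection variable is named and no analysis uses one.

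**The concern.** If the RRT is the screen used before referral, an abnormal red reflex is one way a child becomes a known case. Those eyes were selected by a positive result on the test under study. Diseased eyes that the RRT missed enter only if something else revealed them. A sample that over-represents the first kind gives a higher sensitivity than the RRT would have among all diseased eyes in a screened population.

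Blinding the resident does not remove this, because the selection happened before the child reached the clinic. Enrolling consecutive patients or repeating the reference examination would not remove it either, for the same reason.

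At stake is the step from a clinic estimate to a statement about screening. The Protocol Summary hypothesizes that the RRT is sufficient for anterior pathology, and an upward shift favors that conclusion. The dilation comparison uses the same eyes, so its size can also depend on how they were found.

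**Working it through.** **The plan's own figures.** Section 8.5 gives 59 and 280. Both reproduce as the smallest exact (Clopper-Pearson) sample with total interval width of at most 0.20, divided by the share with or without pathology: 44/0.75 = 58.7, rounded up to 59, and 70/0.25 = 280. They are not in dispute. They matter here because the target precision is ±10 points, and a selection error does not shrink as the sample grows.

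**Inputs from the documents.** Planning sensitivity is 90% (8.5). The newborn screening study cited in 2.1 reports 99.6% for anterior and 4.1% for posterior disease.

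**Assumed inputs.** The documents give no referral data. Assume that every RRT-positive diseased eye reaches the clinic, that a fraction q of RRT-negative ones does, and that an eye gives the same RRT result at screening and in the study. The 70% row is an assumed value with no source in the documents, included to show the middle of the range.

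**Sensitivity.** With true sensitivity s, the clinic value is s / (s + (1 − s)q). For example, at s = 0.90 and q = 0.5: 0.90 / (0.90 + 0.05) = 0.947.

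| True s | q = 0.75 | q = 0.5 | q = 0.25 |
|---|---|---|---|
| 99.6% (cited, anterior) | 99.7% | 99.8% | 99.9% |
| 90% (planning value) | 92% | 95% | 97% |
| 70% (assumed) | 76% | 82% | 90% |
| 4.1% (cited, posterior) | 5% | 8% | 15% |

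At 90% the largest shift is 7 points, inside the planned ±10. At 70% it is 12 points at q = 0.5 and 20 at q = 0.25.

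**If results are not perfectly repeatable.** Let detectability vary between eyes as a beta distribution with mean m and correlation ρ between two tests of the same eye (assumed 0.2 or 0.5). Sensitivity among eyes already positive once is m + ρ(1 − m). This gives 23% or 52% at m = 4.1%, and 92% or 95% at m = 90%. Among eyes already missed once it is m(1 − ρ): about 3% or 2% at m = 4.1%, and 72% or 45% at m = 90%. The first result confirms the upward direction for red-reflex referrals. The second shows that a sample of missed eyes alone would err the other way.

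**Dilation gain.** Three sets of assumptions give different directions.

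- *Stable detectability, with dilation recovering a fixed share of misses and losing no positives.* The gain is multiplied by q / (s + (1 − s)q), which cannot exceed 1. If half of misses are recovered, a true gain of 15 points at s = 70% appears as 12, 9 or 5. At s = 4.1%, 48 points appears as 47, 46 or 43.
- *Beta model, with dilation as a common odds ratio of 2 to 4.* At 4.1% undilated sensitivity the gain is larger in red-reflex referrals (11 to 25 points) than in all cases (1.5 to 6). At 30% it is slightly larger. At 60% and 90% it is smaller; at 90%, ρ = 0.5 and an odds ratio of 4, it is 3.1 against 5.0 points.
- *Simple mixing of two groups.* Let f be the share of red-reflex referrals; the pooled gain is f × (referred gain) + (1 − f) × (other gain). If other cases gain 20 points and referred cases 5, the pooled gain at f = 0.25 is 1.25 + 15 = 16.25. If other cases gain 2 and referred cases 10, it is 2.5 + 1.5 = 4.

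**The case against.** The strongest reply is that the shift is built into the formula. It sets the chance of reaching the clinic at 1 for RRT-positive eyes and below 1 for the rest. The conditions in 5.2 include ptosis and retinopathy of prematurity, which may be found in other ways. If record review over-samples such eyes, the all-cases sensitivity could be too low. This stands: the direction holds only where red-reflex referrals are over-represented, and their share is unknown. It is also a reason to record the route.

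Second, at the documents' own values the shift leaves the expected picture intact: 99.6% barely moves and 4.1% reaches at most 15%. That is fair, although the cited values come from newborns, and this study takes patients under 17.

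Third, the hypotheses differ between sections. The Protocol Summary expects the RRT to be sufficient for anterior disease, while 2.2 expects it to be inadequate for both segments. For posterior disease, upward selection works against the hypothesis, so a poor posterior result would be conservative in this respect. The Protocol Summary also frames the primary aim as the RRT performed in a pediatric ophthalmology clinic, which is narrower than screening. Both points stand. The difficulty arises when the result is used to answer 2.2.

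A reader might also infer that selection necessarily shrinks the gain from dilation. The documents do not support this. They say nothing about how dilation acts on missed eyes, and at the low posterior sensitivity that 2.1 reports the gain may grow.

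**Conclusion.** The point holds as a limit on what the planned estimate can say about screening. Sensitivity is computed within each segment over cases found by any route, the RRT is one plausible route, and nothing planned would show how much of the result reflects earlier selection by the same test.

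The size cannot be fixed from the documents. Under the stated assumptions about q and stable detectability, the upward shift is 2 to 7 points at the planning value, 1 to 11 points at the cited posterior value, and 6 to 20 points at an assumed 70%. The dilation difference may shrink or grow: it shrinks if detectability is stable or undilated sensitivity is high, and may grow if undilated sensitivity is very low.

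It would be tempting to treat the all-cases figure as an upper bound and the figure in eyes found by other routes as a lower bound. Neither is guaranteed. The first may be too low if other routes are over-sampled, and eyes found by other routes may be symptomatic, severe or never screened. This is an inexpensive improvement to the design; it does not invalidate the planned analysis.

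**What to change.** In 6.4, have a team member other than the examiner record from the chart how each qualifying pathology was first detected: abnormal red reflex, another route, or unknown. Section 5.1 already gives access to charts from date of birth, and keeping the examiner out of this step protects the blind.

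In 8.4, report sensitivity and the paired dilation difference by route within each segment, descriptively and with 95% confidence intervals, beside the all-cases figures. Keep red-reflex referrals in the study, because removing them would leave a sample enriched for RRT misses. Do not present the all-cases figure and the figure for other routes as strict bounds. Base any statement that the RRT is sufficient for screening on both. The documents set no threshold for sufficient, so the report should say what standard it applies.

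The cost is one chart field and one table, with no added patients or procedures. Some charts will not show the route, and intervals within routes will be wide. With the 100 cases implied by 5.1 split equally by segment and route (an assumption), each cell has about 25. At 70% the half-width is then 1.96 × √(0.7 × 0.3 / 25), or about 18 points.

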Aims/Objectives: *The primary aim of this study is to determine the sensitivity and specificity of the RRT performed in a pediatric ophthalmology clinic, according to standardized practice guidelines, for detecting both anterior and posterior segment pathology in the pediatric population. The secondary aim of this study is to evaluate the impact of pharmacologic dilation on the sensitivity and specificity of the RRT in detecting anterior and posterior segment pathology in the pediatric population. We hypothesize that the sensitivity and specificity of the RRT will be sufficient for detecting anterior segment pathology but will be insufficient for detecting posterior segment ophthalmologic pathology with or without pharmacologic dilation.*

Study Population: *The study population will include pediatric patients under 17 years old recruited in clinical practice with known anterior or posterior segment pathology as well as patients without anterior or posterior segment pathology. In order to determine sensitivity and*

specificity of anterior and posterior segment pathology separately, we will split the patients with pathology into two groups, anterior and posterior.

Ophthalmology residents who are blinded to the patient's ophthalmologic diagnosis (or lack thereof) will perform the standardized RRT, which includes both a lights on and lights off examination

- Study Site(s):** *Children's National Health System and Fairfax*
- Number of Participants:** *100-200*
- Accrual Ceiling:** *200. We estimate that all consented subjects will be able to participate in this routine vision exam.*
- Study Duration:** *This study is expected to be completed within one year.*
- Subject Duration:** *The subject duration is expected to be one outpatient clinic visit.*

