There is ample evidence in the literature validating the RRT as a useful screening tool for pediatric anterior segment ocular pathology, with consistently high sensitivity and specificity. However, studies describing its utility in detecting posterior segment disease are lacking. Two recent studies have attempted to address this issue. Sun and colleagues used the RRT to screen over 7000 newborns followed by retinal imaging using a Retcam-3 with pharmacologic pupillary dilation. They found that for anterior segment disease, the RRT had a sensitivity of 99.6% (95% CI 97.1%-100%) compared to only 4.1% (95% CI 3.3%-5.1%, $\chi^2 = 1521.382$, $\phi = 0.836$, $P < .001$) for posterior segment pathology. In a similar study, Ludwig and colleagues detected posterior segment pathology in 49 of 194 eyes examined using the Retcam-3 with pharmacologic dilation (sensitivity = 100%); however, no abnormalities were detected in this same set of eyes with the RRT performed by a pediatrician in the newborn nursery (sensitivity = 0%).

Based on these results, there is insufficient evidence that the RRT is an effective screening exam for detecting posterior segment pathology - even with physiologic dilation during the lights off portion of the RRT. It has been established that pupillary size and viewing angle certainly do impact the quality of a posterior segment exam. In a study by Li and colleagues, the rate of tumor detection in a model eye was optimized when viewing at an oblique angle through a maximally dilated pupil of 8 mm. Even under the darkest lighting conditions, physiologic mydriasis will be limited, and especially with introduction of the direct ophthalmoscope light for the RRT. The average infant scotopic pupil size is 3.8 mm \pm 0.9 mm in diameter. When light is shone from ophthalmoscope, pupils usually constrict by 2 mm. Pharmacologic dilation, however, is not currently included as part of the practice pattern guidelines outlining the RRT due to its perceived associated potential risks and side effects.

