3.3 Primary Outcome Measure(s)

Number of eyes with posterior segment pathology correctly identified as having posterior segment pathology and incorrectly identified as not having pathology. Number of healthy eyes correctly identified as being healthy.

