3.4 Secondary Outcome Measure(s)

Number of eyes with anterior segment pathology correctly identified as having anterior segment pathology and incorrectly identified as not having pathology. Number of healthy eyes correctly identified as being healthy.

Section 4: Study Design

Prospective study

Section 5: Study Enrollment and Withdrawal

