8.5 Sample Size

*Our sample size calculation is based on our primary hypothesis. Assuming a 75% prevalence of anterior or posterior segment pathology and a sensitivity of 90% in our sample, a total of **59** patients will be required to construct a two-sided 95% sensitivity confidence interval with a width of at most +/-10%. Under the same assumptions, the sample size needed for a two-sided 95% specificity confidence interval of +/-10% around 80% is **280**. We will take the larger one of these two, which is **280**. The power analysis was carried out using PASS 2019 software.*

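### PPV and NPV are planned without a reference prevalence, in a sample whose disease share is set by recruitment, so crude values cannot be read as screening values

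*Combined protocol and SAP*

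**What the plan says.** Section 8.4, repeated in the Statistical Analysis part of the Protocol Summary, first plans sensitivity and specificity with 95% confidence intervals from contingency tables, for anterior and for posterior pathology. It then adds: "Positive predictive value (PPV), negative predictive value (NPV), and area under ROC curve (AUC) will also be determined". No prevalence, target population, formula or limit on interpretation follows.

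Section 5.1 defines the sample. Children with known pathology are eligible, and "An equal number of age matched participants with a normal anterior and posterior segment exam will be recruited from routine outpatient clinic visits". The numbers are given as "Current estimated number of subjects required for the study is 200 total including 100 controls".

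Three other places bear on the point:
- The Summary (Study Population) says "we will split the patients with pathology into two groups, anterior and posterior", but the size of each group is not fixed anywhere.
- Sections 3.3 and 3.4 count eyes ("Number of eyes with posterior segment pathology correctly identified as having posterior segment pathology"; "Number of eyes with anterior segment pathology correctly identified as having anterior segment pathology"), whereas Sections 5.1 and 8.5 count patients.
- Section 8.5 sizes the study "Assuming a 75% prevalence of anterior or posterior segment pathology" in the sample. This is a sample-size input and is not linked to PPV or NPV.

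**The concern.** Sensitivity is conditional on having disease and specificity on not having it, so neither depends arithmetically on the ratio of cases to controls. PPV and NPV do. When cases and controls are recruited in a chosen ratio, the crude table returns predictive values for that ratio only.

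Here three features of the design would move the crude values even if the test behaved identically: the case-to-control ratio, the unspecified anterior-to-posterior split, and whether eyes or children are counted.

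The study question is about screening. Section 2.1 asks whether the test is good enough to screen with or gives false reassurance, and Section 2.4 hopes to improve screening guidelines. NPV is the figure a reader would take as the measure of false reassurance, and the plan offers no basis for reading it in that setting.

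**Working it through.** **Plan's own figures.** The documents give no PPV or NPV to reproduce. The Section 8.5 sample sizes do reproduce, using an exact (Clopper-Pearson) 95% interval of total width at most 0.20:
- sensitivity 90%: 44 diseased / 0.75 = 58.7, rounded up to 59;
- specificity 80%: 70 non-diseased / 0.25 = 280.

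This supports using 90%, 80% and 75% as the planning inputs. They refer to anterior or posterior pathology combined.

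**Formulas.** With sensitivity Se, specificity Sp and disease share p:
- PPV = Se·p / [Se·p + (1 − Sp)(1 − p)]
- NPV = Sp(1 − p) / [Sp(1 − p) + (1 − Se)p]

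**Same test (Se 0.90, Sp 0.80), different share**

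| Share p | Source | PPV | NPV |
|---|---|---|---|
| 75% | Section 8.5 | 0.675/0.725 = 93.1% | 0.200/0.275 = 72.7% |
| 50% | Section 5.1: 100 cases, 100 controls | 90/110 = 81.8% | 80/90 = 88.9% |
| 25% | Eyes: 100 diseased of 400, if every case is unilateral and fellow eyes count as healthy | 90/150 = 60.0% | 240/250 = 96.0% |
| 5% | Assumed, not in the documents | 0.045/0.235 = 19.1% | 0.760/0.765 = 99.3% |
| 1% | Assumed, not in the documents | 0.009/0.207 = 4.3% | 0.792/0.793 = 99.9% |

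If every case were bilateral, the eye-level share would return to 50%. The first two rows use only shares that the documents state. They serve here as a range.

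**Effect of the anterior-to-posterior split.** Section 8.4 plans a table for each segment. Take one segment's cases against the 100 controls, counted as patients, with an assumed 25, 50 or 75 cases. The shares are 25/125 = 20%, 50/150 = 33.3% and 75/175 = 42.9%. Section 2.1 cites a newborn study in which "the RRT had a sensitivity of 99.6% (95% CI 97.1%-100%) compared to only 4.1" per cent for posterior disease.

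| Cases in the segment (assumed) | PPV/NPV at Se 4.1%, Sp 80% | PPV/NPV at Se 90%, Sp 80% |
|---|---|---|
| 25 | 4.9% / 76.9% | 52.9% / 97.0% |
| 50 | 9.3% / 62.5% | 69.2% / 94.1% |
| 75 | 13.3% / 52.7% | 77.1% / 91.4% |

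Within each column the test is the same and only the recruited split changes. If eyes are counted, all cases are unilateral and fellow eyes count as healthy, the shares become 25/250, 50/300 and 75/350. The Se 4.1% column then reads 2.2%/88.2%, 3.9%/80.7% and 5.3%/75.4%.

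**Two eyes per child in the confidence interval.** This uses the log likelihood-ratio method with Se 0.90, Sp 0.80, 100 cases (all assumed bilateral), 100 controls and prevalence 5%. The standard error of log LR+ is √[(1 − Se)/(Se·n₁) + Sp/((1 − Sp)·n₀)], where n₁ and n₀ are the diseased and non-diseased counts.
- If a child's two eyes carry the same information (n₁ = n₀ = 100): SE 0.203, PPV 19.1% (95% CI 13.7 to 26.1).
- If 200 + 200 eyes are treated as independent: SE 0.143, PPV 19.1% (15.2 to 23.9).
- NPV is 99.3%, with intervals 98.8 to 99.6 and 99.0 to 99.6 respectively.

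**The case against.** The strongest reply is that the plan never says PPV and NPV will be offered as screening values. They appear in no objective, outcome, hypothesis or sample-size calculation, and the screening language in Section 2.1 is about sensitivity and specificity. They could be read simply as descriptions of the recruited sample. This stands as a limit on weight. It does not give the numbers a meaning, because a predictive value at a ratio the investigators chose describes no population a clinician meets, and the plan does not warn the reader of that.

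Some of the illustrations are also open to challenge:
- The 90%/80% inputs are for combined pathology, whereas the planned tables are by segment.
- Sensitivity of 4.1% with specificity of 80% describes a test worse than chance, so the low PPVs in that column partly reflect the pairing. The movement with the split is nevertheless present at 90%/80% as well.
- The 25% eye-level share needs every case to be unilateral, and 5% and 1% are assumptions.

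None of this changes the mechanism, which already shows between the two shares stated in the documents.

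Finally, Bayes-derived values would rest on accuracy in known cases versus normal controls carrying over to unselected children, which this design cannot test. That is a fair caution. It is why the assumption must be stated, and why omitting PPV and NPV or labelling crude values as sample-specific are acceptable alternatives.

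**Conclusion.** The concern holds. Read in the most natural way, the plan would produce PPV and NPV governed by recruitment. Moving only between the two disease shares in the documents shifts PPV by 93.1 − 81.8 = 11.3 percentage points and NPV by 88.9 − 72.7 = 16.2. At an assumed 1% prevalence, the same test has a PPV of 4.3%. These sizes rest on the plan's 90% sensitivity and 80% specificity and on the reading that the values come straight from the contingency tables.

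The problem is confined to PPV and NPV. Sensitivity, specificity and AUC do not depend arithmetically on the case share. The change should be made before analysis, but it does not threaten the primary outcomes.

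**What to change.** Replace the reference to PPV and NPV in Section 8.4 and in the Summary with wording such as:

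> PPV and NPV will be calculated by Bayes' theorem from the estimated segment-specific sensitivity and specificity, before and after dilation, over a pre-specified range of prevalences labelled as assumptions. Their 95% confidence intervals will allow for two eyes per child if eyes are the unit of analysis. The calculation assumes that accuracy in known cases and normal controls transfers to unselected children.

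If no prevalence range can be justified, drop PPV and NPV. Any crude values still reported should be labelled as specific to the recruited sample and not as screening estimates.

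The cost is two or three sentences in each place and no new patient data. The drawbacks are that the range must be justified from outside the protocol and that the transfer assumption cannot be tested in this study.
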